5.3 Lifestyle Considerations

5.3.1 Meals and Dietary Restrictions

For details please refer to Sections [6.1](#) and [6.5](#).

5.3.2 Caffeine, Alcohol, and Tobacco

Not applicable for this protocol.

5.4 Screen Failures

Screen failures are defined as participants who consent to participate in the clinical study but are not subsequently assigned to study intervention. A minimal set of screen failure information is required to ensure transparent reporting of screen failure participants to meet the Consolidated Standards of Reporting Trials (CONSORT) publishing requirements and to respond to queries from regulatory authorities. Minimal information includes demography, screen failure details and any serious AE (SAE).

Individuals who do not meet the criteria for participation in this study (screen failure) may be rescreened once. Whether the participant can repeat the screening will be discussed with the Sponsor. Sponsor's approval of re-screening for a participant must be documented.

Also, for re-screening, the participant has to re-sign the informed consent form, even if it was not changed after the patient's previous screening. The screening failure will be registered in Interactive Voice/Web Response System (IxRS) to close the participant identification number (PID), and re-screening will start again by signing a new informed consent form and being assigned a new PID via IxRS.

6. Study Intervention

Study intervention is defined as any investigational intervention intended to be administered to a study participant according to the study protocol.

Participants will receive nivolumab intravenously on day 1 of every cycle. Nivolumab will be administered as a dose of 480 mg using a 30-min i.v. infusion Q4W.

Regorafenib will be given orally every day for 21 days of each 28-day cycle. Each treatment cycle will be 28 days in duration. Regorafenib will be given as 40 mg tablets q.d. for 21 days of every 28-day cycle (i.e., 21 days on, 7 days off) as a starting dose of 80 mg. If starting dose of 80 mg daily is well tolerated (absence of any grade rash/HFSR or other Grade 2 or higher clinically significant toxicity) dose should be escalated to 120 mg orally daily starting with C2D1. Sponsor should be consulted, if the Investigator decides to not escalate the dose to 120 mg despite meeting the criteria.

When the two study drugs are administered on the same day, regorafenib is to be taken first orally followed by nivolumab infusion.

Regorafenib should be taken within 2 hr after a light meal with approximately 240 mL (8 fluid ounces) of water, preferably in the morning. If necessary, the study drug may be taken at different times of the day, but there should be consistency with respect to dosing intervals (the recommendation is to have at least a 20 hr interval between doses). Tablets should not be chewed. If a dose of regorafenib is missed, the missed dose should not be made up for (vomited tablets cannot be made up), and the next dose should be taken at the regular time. The subsequent dose of regorafenib should not be doubled. The investigator should be informed if the dose of regorafenib taken exceeded the scheduled dose.

On days when pre-dose PK blood samples will be collected ([Table 8–2](#)), participants will take the morning dose of regorafenib at the clinic after all required samples are collected. On days PK samples are not required, regorafenib can be taken at home or in clinic.

Participants will continue treatment until disease progression as defined by RECIST v1.1, unacceptable toxicity or consent withdrawal, withdrawal from the study at the discretion of the investigator or his/her designated associate(s) or any other withdrawal criteria are met. Treatment beyond radiological progression is possible if the participant is still benefiting from treatment. In order to continue treatment after initial documentation of disease progression, participant must be re-consented. In case of treatment interruption or discontinuation due to Nivolumab or Regorafenib related toxicities participants may continue treatment with either Nivolumab or Regorafenib single agent respectively.

Participants who complete 24 infusions of nivolumab (after approximately 2 years of treatment) need to discontinue treatment. Regorafenib treatment can be continued until clinical disease progression, or unacceptable toxicity, or any other withdrawal criteria are met.

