4.1.2 Treatment Phase

Participants will be treated with nivolumab i.v. given on D1 and regorafenib orally every day for 21 days in a 28-d cycle. Nivolumab will be administered as a flat dose of 480 mg using a 30 min i.v. infusion Q4W. Regorafenib will be given at a starting dose of 80 mg for 21 days of every 28-day cycle (i.e., 21 days on, 7 days off). If the starting dose of 80 mg daily is well tolerated (absence of any grade rash/HFSR or other Grade 2 or higher clinically significant toxicity) the dose should be escalated to 120 mg orally daily starting with C2D1. Dose modification guidelines for dose reduction in case of toxicity are detailed in Section 6.6. The Sponsor should be consulted, if the Investigator decides to not escalate the dose to 120 mg despite meeting the criteria.

Participants will continue treatment until disease progression as defined by RECIST v1.1, unacceptable toxicity or consent withdrawal, withdrawal from the study at the discretion of the investigator or his/her designated associate(s) or any other withdrawal criteria are met. Treatment beyond radiological progression as per Response evaluation criteria in solid tumors for trials testing immunotherapeutics (iRECIST) is possible if the participant is still benefiting from treatment. For details please refer to Section 8.1.

Patients who complete 24 infusions of nivolumab (after approximately 2 years of treatment) need to discontinue treatment. Regorafenib monotherapy treatment can be continued beyond 2 years until discontinuation criteria are met.

During the study, participants will undergo evaluations for safety, efficacy, and tissue and blood for biomarker will be collected. Tumor assessments will be at baseline, every 8 weeks \pm 7 d for the first year and thereafter every 12 weeks \pm 14 d until progressive disease. Treatment with individual drugs (regorafenib or nivolumab) may continue on schedule even if the other drug is interrupted or permanently discontinued due to toxicity.

Primary endpoint of the study is ORR measured by RECIST v1.1 as determined by investigator. Scans will be prospectively collected and stored by a vendor in case independent central review is needed.

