- If all values remain stable for 2 full cycles, dose re-escalation may be considered at the discretion of the Investigator. After re-escalation AST, ALT, bilirubin should be checked 2x/week for 2 weeks, followed by weekly assessments for at least 4 weeks.
- Exception: participants with Gilbert's syndrome who develop elevated transaminases should be managed as per the above outlined recommendations for the respective observed elevation of ALT and/or AST.

The dose modification can occur independently for the 2 drugs used if toxicity can be clearly attributed to one of the drugs. Resumption of regorafenib dosing is not required to receive further nivolumab dosing and vice versa. Treatment with individual drugs (regorafenib or nivolumab) may continue on schedule even if other drug is interrupted or permanently discontinued due to toxicity.

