6.6.2 Toxicity Management and Dose Modification Recommendations for Nivolumab

AEs (both non-serious and serious) associated with nivolumab exposure may represent an immunologic etiology. These AEs may occur shortly after the first dose or several months after the last dose of treatment. Therefore, early recognition and initiation of treatment is critical to reduce complications.

There will be no dose reductions for nivolumab. Treatment can be delayed for nivolumab related AEs. If the criteria to resume treatment are met, the subject should restart treatment at the next scheduled time point per protocol.

Nivolumab administration should be delayed for the following:

- Grade 2 non-skin, drug-related AE, with the exception of fatigue
- Grade 2 drug-related creatinine, AST, ALT and/or Total Bilirubin abnormalities
- Grade 3 skin, drug-related AE
- Grade 3 drug-related laboratory abnormality, with the following exceptions:
 - Grade 3 lymphopenia or asymptomatic amylase or lipase does not require dose delay
 - Grade ≥ 3 AST, ALT, Total Bilirubin will require dose discontinuation (see Section 6.6.2.1)
- Any adverse event, laboratory abnormality, or intercurrent illness which, in the judgment of the investigator, warrants delaying the dose of study medication.

There are no recommended dose modifications for hypothyroidism or hyperthyroidism. Interrupt or slow the rate of infusion in participants with mild or moderate (Grade 1-2)

infusion reactions. Discontinue nivolumab in participants with severe or life-threatening infusion reactions (Grade 3-4) (see Section 6.6.2.4).

Participants who require delay of nivolumab should be re-evaluated weekly or more frequently if clinically indicated and resume nivolumab dosing when re-treatment criteria are met (see Section 6.6.2.2). The dose modification can occur independently for the 2 drugs used if toxicity can be clearly attributed to one of the drugs. Resumption of regorafenib dosing is not required to receive further nivolumab dosing and vice versa. Treatment with individual drugs (regorafenib or nivolumab) may continue on schedule even if other drug is interrupted or permanently discontinued due to toxicity.

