7.1 Discontinuation of Study Intervention

Withdrawal from study treatment period

Patients **MUST** be withdrawn from the study treatment combination if any of the following occurs:

- At their own request or at the request of their legally acceptable representative. At any time during the study and without giving reasons, a patient may decline to participate further. The patient will not suffer any disadvantage as a result.
- If, in the investigator's opinion, continuation of the study treatment would be harmful to the patient's well-being.
- Clinical progression as per iRECIST (every effort should be made to obtain radiological confirmation of disease progression [PD] during active FU). Note: In cases where radiographic evaluation is not possible, clinical progression may be used. Clinical progression is based on the judgment of the investigator (e.g., defined as worsening of the ECOG PS ≥ 3 or symptomatic deterioration including increase in liver function tests).
- The development of a second primary malignancy that requires a different treatment.
- Development of any intercurrent illness or situation which may, in the judgment of the investigator, affect assessments of clinical status and study endpoints to a relevant degree.

- Severe allergic reactions, such as exfoliate erythroderma, anaphylaxis, or vascular collapse.
- Start of subsequent systemic anti-cancer treatment
- Use of illicit drugs or other substances that may, in the opinion of the investigator or their designated associate(s), have a reasonable chance of contributing to toxicity or otherwise confound the results.
- Pregnancy
- Participant lost to follow-up
- Death
- *Withdrawal of regorafenib only:*
 - Patients who halt therapy for more than 28 consecutive days - including the 1 week drug holiday. However, continuation of regorafenib may be considered if, in the investigator's opinion, the patient may continue to benefit from the regorafenib treatment, and after consultation with sponsor.
 - Unacceptable toxicity, i.e., event requiring permanent discontinuation of regorafenib according to dose modification guidance in Section 6.6.
- *Withdrawal of nivolumab only:*
 - Patients who experience a delay of more than 10 weeks to receive the subsequent nivolumab infusion due to treatment related toxicity (see exceptions in Section 6.6.2.1)
 - Patients who complete 24 infusions of nivolumab (after approximately 2 years of treatment)

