 - Unacceptable toxicity, i.e. event requiring permanent discontinuation of nivolumab according to dose modification guidance in Section 6.6.2.1.

Withdrawal from active FU

Participants *must* be withdrawn from active FU if any of the following occurs:

- At their own request or at the request of their legally acceptable representative. At any time during the study and without giving reasons, a participant may decline to participate further. The participant will not suffer any disadvantage as a result.
- Radiologically confirmed PD is observed and/or clinical progression occurs (provided safety visits have been performed)
- Start of subsequent systemic anti-cancer treatment (provided safety visits have been performed)
- Development of a second primary malignancy that requires a different treatment
- Substantial non-compliance with the requirements of the study
- Withdrawal of consent to active FU visits

- If, in the investigator's opinion, continuation of the active FU visits would be harmful to the participant's well-being
- Participants lost to FU
- Death

Withdrawal from long-term FU

Participants *must* be withdrawn from long-term FU if any of the following occurs:

- Withdrawal of consent to long-term FU
- Participants lost to FU
- Death

Participants **MAY** be withdrawn from the study treatment combination for the following reasons:

- At the specific request of the sponsor and in liaison with the investigator (e.g., obvious non-compliance, safety concerns).
- Withdrawal of nivolumab only: discontinuation of nivolumab may be considered for participants who have attained a confirmed complete response (CR), that have been received at least 8 infusions (32 weeks) of nivolumab and had at least 2 infusions with nivolumab beyond the date when the initial CR was declared.

Discontinuation of study intervention for abnormal liver function should be considered by the Investigator when a participant meets one of the conditions outlined in [Table 6–6](#) or if the Investigator believes that it is in best interest of the participant.

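### Protocol Section 6, read literally, permits continuing the drug that caused the toxicity; Sections 4.1.2, 6.6 and 7.1 pair the drugs the other way

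*Protocol*

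**What the plan says.** The sentence stands in Protocol Section 6 (Study Intervention), in the paragraph on how long treatment continues. It opens "In case of treatment interruption or discontinuation" and goes on "due to Nivolumab or Regorafenib related toxicities participants may continue treatment with either Nivolumab or Regorafenib single agent respectively".

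Four other places in the current protocol deal with the same situation:

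- Section 4.1.2, on treatment with the individual drugs: each "may continue on schedule even if the other drug is interrupted or permanently discontinued due to toxicity".
- Section 6.6.1, closing paragraph: each drug "may continue on schedule even if other drug is interrupted or permanently discontinued due to toxicity". Section 6.6.2 repeats this. Both sections also state: "Resumption of regorafenib dosing is not required to receive further nivolumab dosing and vice versa".
- Section 6.6.2.1 lists the drug-related events after which nivolumab is permanently discontinued.
- Section 7.1 sets out, drug by drug, when each is withdrawn alone. For regorafenib the trigger is an "event requiring permanent discontinuation of regorafenib according to dose modification guidance in Section 6.6". For nivolumab it is an "event requiring permanent discontinuation of nivolumab according to dose modification guidance in Section 6.6.2.1".

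**The concern.** Which drug a participant may stay on after a toxicity that stopped treatment is a safety instruction. Section 6 is the main treatment section, so a sentence there carries weight with sites. At this sentence there is no reference to Section 6.6 or 7.1, and the protocol gives no order of precedence between its sections.

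Two things are at stake. The first is conduct: one section permits what others withdraw. The second is the standard against which conduct is judged. If a site kept a participant on the drug that had been stopped, a monitor would find one section allowing it and others forbidding it. The SAP (Section 4.7) relies on a final list of important deviations, and that list needs a single rule to apply.

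**Working it through.** No figure is in dispute, so the check sets the passages side by side.

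**Step 1: the literal mapping in Section 6.** The first list (source of toxicity) is nivolumab, regorafenib. The second list (single agent that may continue) is nivolumab, regorafenib. *Respectively* joins first to first and second to second.

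| Toxicity from | Section 6, literal: may continue | Sections 4.1.2, 6.6.1, 6.6.2: may continue | Sections 6.6.2.1 and 7.1, where the stopping rule is met |
|---|---|---|---|
| Nivolumab | Nivolumab alone | The other drug, regorafenib | Nivolumab is withdrawn |
| Regorafenib | Regorafenib alone | The other drug, nivolumab | Regorafenib is withdrawn (7.1) |

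In both rows the second column names the opposite drug from the third. Crossing the pairs would require one of the two lists to be in reverse order, and neither is.

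**Step 2: interruption and discontinuation taken separately.** The Section 6 sentence covers both.

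- *Interruption.* Section 6.6.2.2 lets nivolumab resume once its criteria are met, and Section 6.6.2 does not make this depend on regorafenib resuming. The regorafenib tables in Section 6.6.1 likewise provide for restarting. A participant can therefore end up on the drug that was held, as a single agent, without breaching Section 6.6. Here the Section 6 sentence is misleading, but it is not strictly incompatible with the rest.
- *Permanent discontinuation.* Section 7.1 lists withdrawal of the single drug among the events for which withdrawal is mandatory. A permission to continue that same drug cannot be squared with it. Sections 6.6.2.1 and 7.1 contain specific exceptions that depend on discussion or agreement with the sponsor. Those are narrow and conditional, whereas the Section 6 permission is general.

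**Step 3: is the sentence still live?** The original protocol is dated 12 July 2019 and Amendment 2 is dated 18 November 2020 (Section 12.1). That is 366 + 129 = 495 days, or 495 / 7 = 70.7 weeks. On a four-weekly schedule the 24th nivolumab infusion falls at 23 × 4 = 92 weeks after the first. Assuming nobody was treated before the original protocol date and infusions kept to schedule, no participant had reached the nivolumab limit when the current text was issued. Regorafenib may go on beyond that limit. The sentence therefore still applied to anyone on treatment.

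**Step 4: does the primary analysis depend on it?** The full analysis set is everyone with at least one dose (Protocol Section 9.3). The test of 5% against a target of 17%, with 70 participants and 8 responders needed, uses neither the continuation rule nor the drug on which a participant continues. Nothing in that calculation changes.

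**The case against.** The best reply is that this is an editorial slip with no realistic second reading. Section 4.1.2 states the cross-drug rule earlier in the protocol, and Sections 6.6.1 and 6.6.2 repeat it. Section 7.1 is mandatory while Section 6 is permissive, so a site that follows 6.6 and 7.1 breaches nothing in Section 6. Permission to continue a drug just discontinued for its own toxicity is odd enough that an investigator would probably see the mistake. Most of this stands, and it limits the weight of the point. It does not remove the contradiction: the permission is in current text, and nothing in Section 6 withdraws it.

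A reader might also infer more than the documents support:

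- *That a participant stopped for nivolumab toxicity must stay on nivolumab.* The sentence allows this and does not require it.
- *That this is the first instruction sites meet.* Section 4.1.2 comes before it.
- *That the passages can never all be followed.* For interruptions they can, as Step 2 shows.
- *That a countable group is at risk.* No rate of single-drug stops is given. At an assumed 10% to 30% of 70 treated participants the count would be 0.10 × 70 = 7 to 0.30 × 70 = 21. That would count the people to whom the sentence applies, not people given the wrong drug.
- *That the safety data are distorted.* Action taken is recorded separately for each drug (Protocol Section 8.3), and dose modification is summarised for each treatment separately (SAP Section 6.5.1). Those records show what happened. No bias from this sentence is demonstrated.

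**Conclusion.** The point holds as an internal inconsistency: the Section 6 sentence is wrong as written. Its literal pairing is the reverse of that in Sections 4.1.2, 6.6.1 and 6.6.2. For permanent discontinuation it also conflicts directly with Sections 6.6.2.1 and 7.1. It is probably a drafting slip, but one on a safety instruction in operative text, so it should be corrected and not left to readers to resolve.

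Its size cannot be put as a number of participants, and no harm or misdosing is documented. The objective response rate analysis, type-I error, power and sample size are unaffected. The conclusion rests on the ordinary meaning of *respectively* and on the current protocol text, with no numerical assumption. It takes no position on the clinical rule itself.

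**What to change.** Reconcile the Section 6 sentence with Sections 4.1.2, 6.6.1, 6.6.2, 6.6.2.1 and 7.1, so that all of them identify the same drug as the one that may continue. One way is to delete *respectively* and the paired lists and refer the reader to Sections 6.6 and 7.1. The reworded sentence should treat interruption and permanent discontinuation separately, since the other sections do. The sponsor's clinical team must confirm the intended rule before the text is changed.

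The cost is one sentence in the next amendment, or a clarification letter to sites that still have participants on treatment. No change to data collection, analysis or sample size is needed.

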6.1 Study Intervention(s) Administered

Table 6–1: Administration of Study Intervention

Study Intervention	Regorafenib	Nivolumab
Type	small molecule drug (MKI)	monoclonal antibody, biologic
Dose Formulation	tablet	concentrate for solution for infusion
Unit Dose Strengths	40 mg / tablet	240 mg / 24 mL vial (10 mg/mL)
Dosage Levels	2x 40 mg tablets every day (q.d.) for 21 days of every 28-day cycle (i.e. 21 days on, 7 days off) as a starting dose of 80 mg. If the starting dose is well tolerated dose should be escalated to 120 mg (3x40 mg tablets) starting with C2D1.	480 mg (2x240 mg / 24 mL vials) on D1 of each cycle
Route of Administration	oral	i.v. infusion
IMP and NIMP	IMP	IMP
Sourcing	Regorafenib will be provided centrally by the Sponsor.	Nivolumab will be provided centrally by the Sponsor.
Packaging and Labeling	Regorafenib is available in high density polyethylene bottles with a white child resistant closure and induction seal. The packaging configuration is 30 tablets Regorafenib 40 mg and a 3 g desiccant per bottle of Regorafenib 40 mg. The bottles will be labeled as required per country requirement.	Nivolumab will be provided in glass injection vial. Each glass injection vial will be labeled as required per country requirement.

Abbreviations: IMP = investigational medicinal product; i.v. = intravenous; MKI = multikinase inhibitor; NIMP = non-investigational medicinal product

6.2 Preparation/Handling/Storage/Accountability

The Investigator (or designee) must confirm appropriate temperature conditions have been maintained during transit for all study intervention received and any discrepancies are reported and resolved before use of the study intervention.

Study intervention should be stored in a secure locked location and at the recommended label temperature for the regorafenib 40 mg tablets in bottles and the nivolumab 240 mg / 24 mL vials.

Note: The regorafenib bottle contains a desiccant. Once the drug has been received it has to be kept in a secure, dry location. The tablets have to be stored in the original bottle according to the labelled storage advice. The tablets have to be stored in the original pack provided in order to protect from moisture and swallowed immediately after they have been taken out. The bottle has to be kept tightly closed after first opening and the desiccant has to remain in the bottle. Once the bottle is opened, tablets should be used within 7 weeks. Any unused tablets must be returned to study site by the patient. Beyond that, no special precautions are required, when handling the study drug.

The personnel will use the study intervention only within the framework of this clinical study and in accordance with this protocol. Only participants enrolled in the study may receive study intervention and only authorized site staff may supply or administer study intervention. All study intervention must be stored in a secure, environmentally controlled, and monitored (manual or automated) area in accordance with the labeled storage conditions with access limited to the Investigator and authorized site staff. The Investigator, institution, or the head of the medical institution (where applicable) is responsible for study intervention accountability,

reconciliation, and record maintenance (i.e., receipt, reconciliation, and final disposition records).

Further guidance and information for the final disposition of unused study interventions are provided in a separate document.

